4.5.2.1 Intra-subject Dose Escalation

Intra-subject dose escalation of BMS-986183 monotherapy or BMS-986183 and nivolumab combination therapy is not permitted.

4.5.2.2 Management Algorithms for Immuno-oncology Agents: BMS-986183 and Nivolumab Combination Therapy Only

Immuno-oncology (I-O) agents are associated with AEs that can differ in severity and duration from AEs caused by other therapeutic classes. Nivolumab is considered an I-O agent in this protocol. Early recognition and management of AEs associated with I-O agents may mitigate severe toxicity. Management algorithms have been developed to assist investigators in assessing and managing the following groups of AEs:

- GI
- Renal
- Pulmonary
- Hepatic
- Endocrinopathy
- Skin
- Neurological

The above algorithms are found in the nivolumab IB⁷³ and Appendix 2 of this protocol. In addition to the guidance provided in these algorithms, it is recommended that consultation with a nephrologist be obtained for subjects with Grade 2 or 3 renal I-O-related AEs. Also, the use of infliximab for I-O-related AEs has the most data for treatment of colitis/diarrhea, whereas use in other AEs has not been well established. Infusion reaction management is provided in Section 3.7.

Immune-mediated adverse reactions are specific events occurring within 100 days of the last dose [which includes pneumonitis, diarrhea/colitis, hepatitis, nephritis/renal dysfunction, rash, and endocrine abnormalities (adrenal insufficiency, hypothyroidism/thyroiditis, hyperthyroidism, diabetes mellitus, and hypophysitis)], regardless of causality, for which subjects received immunosuppressive medication for treatment of the event. The exception to the immunosuppressive medication for is endocrine criteria **IMARs** events hyperthyroidism. diabetes (hypothyroidism/thyroiditis, hypophysitis, mellitus. adrenal insufficiency), which are included regardless of treatment since these events are often managed without immunosuppression.

4.5.3 Protocol-Specific Recommendation for Management of Hepatic Events

Subjects with advanced HCC generally have underlying cirrhosis with decreased hepatic function. They may also have a concomitant chronic viral infection. For CA015003, the upper limits for inclusion were therefore adjusted to account for baseline liver dysfunction. Subjects with AST or ALT elevations within the CTCAE Grade 2 range can be enrolled. This requires a protocol-specific approach for the management of hepatic events, outlined as follows.

For subjects in BMS-986183 and nivolumab dose escalation (Part 3) and BMS-986183 and nivolumab dose expansion (Part 4), the protocol-specific approach for the management of hepatic events is as follows:

• If AST or ALT levels do not improve with a dose delay of 3 to 5 days or if the levels worsen, initiate steroid therapy at 0.5 to 2 mg/kg/day methylprednisolone or oral equivalent.

- For ALT or AST levels $> 8 \times$ ULN, initiate steroid therapy promptly at 1 to 2 mg/kg/day methylprednisolone or oral equivalent.
- For all subjects initiating steroids, consult the BMS Medical Monitor within 24 hours after initiation of steroids. Gastroenterology consult is recommended.
- If AST or ALT levels do not improve within 3 to 5 days or the levels worsen after the start of steroid therapy, discuss with the BMS Medical Monitor the possibility of adding mycophenolate mofetil at 1 g twice daily.
- Tapering of steroids can start once AST or ALT levels have declined by 1 CTCAE grade. Taper steroids slowly over no less than 1 month.

As outlined in Section 4.5.3.2, nivolumab and BMS-986183 combination therapy may resume when AST or ALT have returned to near baseline unless the criteria for permanent discontinuation are reached (Section 4.5.6).

4.5.3.1 Criteria for Dose Modifications or Delay for Changes in AST, ALT or Total Bilirubin

Subjects who experience the following must have dose of study drug delayed:

- If a subject has a baseline AST, ALT or total bilirubin that is within normal limits, delay dosing for drug-related ≥ Grade 2 toxicity (2 grade shift)
- If a subject has baseline AST, ALT or total bilirubin within the Grade 1 toxicity range, delay dosing for drug-related ≥ Grade 3 toxicity (2 grade shift)
- If a subject has baseline AST, ALT or total bilirubin within the Grade 2 toxicity range, delay dosing for a 2-fold drug-related increase in AST, ALT or total bilirubin or for AST or ALT values 8 × ULN (whichever is lower)
- Hepatic DLT as defined in Section 4.5.1.

It is recommended to monitor elevations in AST, ALT or total bilirubin approximately every 3 days until levels peak and begin to decline. BMS-986183 dosing can be resumed where treatment criteria are met (Section 4.5.3.2)

If AST, ALT or total bilirubin levels do not improve with a dose delay of 3 to 5 days or if the levels worsen, or for ALT or AST levels $> 8 \times ULN$, a gastroenterology/hepatology consult and discussion with BMS medical monitor is recommended.

4.5.3.2 Criteria to Resume Treatment for Elevations of AST or ALT or Total Bilirubin

Subjects who experience the following are eligible to resume study drug administration:

- Subjects with baseline Grade 1 AST, ALT, or total bilirubin who require dose delays for reasons other than a study drug-related hepatic event may resume treatment in the presence of Grade 2 AST, ALT, or total bilirubin.
- Subjects who require dose delays for drug-related increased AST, ALT, or total bilirubin may resume treatment when hepatic parameters are at baseline or CTCAE Grade 1 and after discussion with BMS Medical Monitor.

• Subjects with AST, ALT, and bilirubin values meeting discontinuation parameters (Section 4.5.6) should have treatment permanently discontinued.

Subjects meeting criteria to resume treatment will undergo dose modification with BMS-986183 as outlined in Section 4.5.2.

4.5.4 Dose Delays Due to Toxicity

Subjects who experience the following must have study drug held:

- Potential DLTs (DLT per definition, are related to study drug), until DLT relatedness is defined. In BMS-986183 and nivolumab dose escalation (Part 3) and BMS-986183 and nivolumab dose expansion (Part 4), every attempt must be made to assign relationship to BMS-986183, to nivolumab, or to both.
- Elevated AST or ALT as defined in Section 4.5.3.1.
- Grade 1 Troponin T or I elevation until confirmation (until repeat Troponin is $\leq 1 \times$ ULN) within 24 hours. (Subjects with repeat Troponin I or T > 1× ULN will be discontinued.)
- AE, laboratory abnormality, or concurrent illness that, in the judgment of the Investigator, warrants delaying the dose of study drug.

Nivolumab in combination with BMS-986183 administration should be delayed for the following:

- Any > Grade 2 non-skin, drug-related AE, with the exception of fatigue
- Any > Grade 3 skin, drug-related AE
- Any > Grade 3 drug-related laboratory abnormality (excluding AST/ALT or total bilirubin), with the following exceptions:
 - Grade 3 lymphopenia does not require dose delay.
 - Any \geq Grade 3 drug-related amylase or lipase abnormality that is not associated with symptoms or clinical manifestations of pancreatitis does not require dose delay.
- Any AE, laboratory abnormality, or intercurrent illness that, in the judgment of the investigator, warrants delaying the dose of study medication

Subjects who require delay of BMS-986183 and/or nivolumab should be re-evaluated weekly or more frequently if clinically indicated and resume study drug dosing when retreatment criteria are met.

Subjects eligible to resume study therapy can resume treatment(s) after at least 21 days from the last dose. Subjects who meet criteria listed in Section 4.5.6 are required to permanently discontinue study drug. All other subjects will be permitted to resume therapy with study drug following resolution of the AE as described in Section 4.5.2.

Extensions to the period of dose delays > 6 weeks may be granted for individual subjects on a case-by-case basis after specific consultation and agreement between the investigator and BMS medical monitor in settings where benefit/risk may justify continued study therapy (eg, subject deriving clinical benefit who requires prolonged steroid taper for the management of non-DLT drug related AEs, or experiences delays for the management of a non-drug-related AE).

The end of cycle tumor assessments will continue every 6 weeks (Q6W; ± 1 week) relative to the subject's first dose regardless of any treatment delay incurred.

4.5.5 Criteria to Resume Treatment

Subjects experiencing AEs not meeting the criteria for permanent discontinuation as outlined in Section 4.5.6 may resume treatment with study medication under the following criteria:

Subjects may resume treatment after dose modification with study drug when the drug-related non-DLT AE(s) resolve to \leq Grade 1 or baseline value with the following exceptions:

- Subjects may resume treatment in the presence of Grade 2 fatigue
- Subjects who have not experienced a Grade 3 drug-related skin AE may resume treatment in the presence of Grade 2 skin toxicity
- For AST/ALT/total bilirubin elevation (see hepatic criteria in Section 4.5.3.2)
- For subjects in BMS-986183 and nivolumab dose escalation (Part 3) and BMS-986183 and nivolumab dose expansion (Part 4), drug-related pulmonary toxicity, diarrhea, or colitis must have resolved to baseline before treatment is resumed. Subjects with persistent Grade 1 pneumonitis after completion of a steroid taper over at least 1 month may be eligible for retreatment if discussed with and approved by the BMS Medical Monitor.
- Subjects in BMS-986183 and nivolumab dose escalation (Part 3) and BMS-986183 and nivolumab dose expansion (Part 4) with drug-related endocrinopathies adequately controlled with only physiologic hormone replacement may resume treatment after consultation with the BMS Medical Monitor. Adrenal insufficiency requires discontinuation regardless of control with hormone replacement.
- If the criteria to resume treatment are met, the subject should restart treatment after at least 21 days from the last dose.
- Tumor assessments should continue as per protocol even if dosing is delayed.

The consideration to re-initiate study therapy under these exceptions will be made on a case-bycase basis after considering the overall benefit/risk profile and in consultation between the investigator and the Sponsor.

- Any dosing delay lasting > 6 weeks from the previous dose requires discontinuation, with the following exceptions:
 - Dosing delays to allow for prolonged steroid tapers to manage drug-related AEs are allowed.
 - Dosing delays lasting > 6 weeks from the previous dose that occur for non-drug-related reasons may be allowed if approved by the BMS Medical Monitor.
 - Prior to re-initiating treatment in a subject with a dosing delay lasting > 6 weeks, the BMS Medical Monitor must be consulted. Tumor assessments should continue as per protocol even if dosing is delayed. Periodic study visits to assess safety and laboratory studies should also continue Q6W or more frequently if clinically indicated during such dosing delays.

4.5.6 Guidelines for Permanent Discontinuation

Subjects will be required to permanently discontinue study drug for the following criteria:

- Clinical deterioration, as assessed by the investigator
- Progressive disease (PD)
- For subjects in BMS-986183 and nivolumab dose escalation (Part 3) and BMS-986183 and nivolumab dose expansion (Part 4), any Grade 2 drug-related uveitis, eye pain, or blurred vision that does not respond to topical therapy and does not improve to Grade 1 severity within the retreatment period OR requires systemic treatment
- Any drug-related AE occurring at any time that meets DLT criteria as outlined in Section 4.5.1 will require discontinuation of nivolumab and/or dose modification of BMS-986183.
- Grade 3 drug-related uveitis, pneumonitis, bronchospasm, hypersensitivity reaction, neurological toxicity, or infusion reaction of any duration requires discontinuation.
- Any Grade 3 non-skin, drug-related AE lasting > 7 days or recurs.
- Any Grade 3 or 4 AE that meets DLT criteria as outlined in Section 4.5.1; however, an exception may be made for the following upon consultation between the investigator and BMS medical monitor:
 - Grade 3 infusion reaction that returns to Grade 1 in less than 6 hours
 - Grade 3 diarrhea, nausea, vomiting, or abdominal pain that returns to Grade 1 or baseline within 3 days with medical intervention
 - Grade 3 pruritus or rash that returns to Grade 1 or baseline within 7 days with medical intervention
 - Grade 3 or 4 electrolyte imbalances/abnormalities that are not associated with clinical sequelae and are corrected with supplementation/appropriate management within 72 hours
 - Grade 4 neutropenia < 7 days in duration
 - Grade 4 lymphopenia or leukopenia
 - Grade 3 or 4 amylase or lipase abnormalities that are not associated with symptoms or clinical manifestations of pancreatitis
 - Grade 3 or 4 drug-related endocrinopathy AEs, such as hyper- or hypothyroidism, or glucose intolerance, which resolve or are adequately controlled with physiologic hormone replacement (corticosteroids, thyroid hormones) or glucose-controlling agents, respectively, may not require discontinuation after discussion with and approval from the BMS Medical Monitor. Adrenal insufficiency requires discontinuation regardless of control with hormone replacement.
 - Grade 3 drug-related laboratory abnormalities do not require treatment discontinuation except:
 - Grade 3 drug-related thrombocytopenia > 7 days or associated with bleeding requires discontinuation
 - AST or ALT > $10 \times ULN$ for > 2 weeks
 - AST or ALT > $15 \times$ ULN irrespective of duration

- Total bilirubin > 8 × ULN irrespective of duration for subjects with elevated bilirubin at study entry or > 5 × ULN for those with normal total bilirubin at entry
- Concurrent AST or ALT > 3 × ULN and total bilirubin > 5 × ULN for subjects entering treatment with a normal bilirubin and up to 8 × ULN for subjects with elevated bilirubin
- Any AE, laboratory abnormality, or intercurrent illness that, in the judgment of the investigator, presents a substantial clinical risk to the subject with continued dosing of study treatment(s).
- Confirmed CR
- Completion of 1 year (17 cycles, with 21 days/cycle) of treatment

All subjects who discontinue IP should comply with protocol-specified follow-up procedures as outlined in Section 5.1. The only exception to this requirement is when a subject withdraws consent for all study procedures including post-treatment study follow-up or loses the ability to consent freely (eg, is imprisoned or involuntarily incarcerated for the treatment of a psychiatric or physical illness).

If study treatment is discontinued prior to the subject's completion of treatment, the reason for the discontinuation must be documented in the subject's medical records and entered on the appropriate CRF page.

If the investigator determines a possible favorable benefit/risk ratio that warrants continuation of study drug(s), a discussion between the investigator and the BMS Medical Monitor/designee must occur including during BMS-986183 and nivolumab combination therapy. If there is toxicity requiring discontinuation and the toxicity is considered related to 1 study drug while clinical benefit has been observed (eg, pneumonitis due to nivolumab), treatment with the study drug to which the toxicity is attributed must be discontinued, but may be resumed for the other study drug, but only after discussion and agreement with the BMS Medical Monitor (or designee).

The consideration to re-initiate study therapy under these exceptions will be made on a case-by-case basis after considering the overall benefit/risk profile and in consultation between the investigator and the study Sponsor.

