4.5.2 Guidelines for Dose Modifications

Subjects will be monitored continuously for AEs while on study therapy. Subjects will be instructed to notify their physician immediately for any and all AEs. For the purposes of subject management, drug-related AEs occurring at any time that meet the DLT definition will lead to dose interruption, dose modifications, and/or permanent discontinuation of study drug as defined in Table 4.5.2-1 and in this section. The criteria presented in this section and Table 4.5.2-1 for dose modifications and delays are meant as general guidelines:

- Subjects will continue to receive therapy as long as they have not had disease progression or drug-related AE requiring dose modification as described below.
- Dose modification, interruption, or delay may occur in the setting of lower grade AE and/or be more conservative than indicated in Table 4.5.2-1 based on the clinical judgment of the investigator, and in consultation with the Sponsor/medical monitor.
- Dose reductions should be to the previous lower dose level.
- If several AEs of varying grade or severity occur simultaneously, the dose modification applied should be the greatest reduction applicable.
- Assessment of causality (chronology, confounding factors such as disease, concomitant medications, diagnostic tests and previous experience with the agent) must be determined and documented by the investigator, prior to dose modification.
- If the same > Grade 3 nonhematologic AE recurs despite a dose reduction, a second dose reduction vs discontinuation of the subject from further protocol therapy will be discussed and agreed upon by the Sponsor/medical monitor and investigators.
- Subjects who experience a Grade 4 nonhematologic AE, except for Grade 4 electrolyte abnormalities (see Table 4.5.2-1), will not receive additional protocol-related therapy and will be removed from study unless discussed and agreed upon by the Sponsor/medical monitor and investigators that it is in the best interest of the subject to receive additional therapy with BMS-986183 (for example, if the subject has demonstrated a response to therapy).
- No more than 2 dose reductions will be allowed per subject. If a third dose reduction is required the subject must discontinue study drug. Dose re-escalation after a dose reduction may occur

in limited circumstances (such as a change in attribution of an AE) after discussion and agreement of the Sponsor/medical monitor and investigators.

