- For an AE requiring dose modification, BMS-986183 should be interrupted to allow recovery from the AE. Re-initiation of study drug cannot occur until AE decreases to ≤ Grade 1 or baseline assessment. In case of delayed recovery to ≤ Grade 1 or baseline (except for alopecia or fatigue) from treatment-related AEs that results in a delay of treatment for > 6 weeks, the subject will not receive additional protocol-related therapy and will be removed from study unless discussed and agreed upon by the Sponsor/medical monitor and investigators that it is in the best interest of the subject to receive additional therapy with BMS-986183 (for example, if the subject has demonstrated a response to therapy).
- During the DLT evaluation period, if a subject is dose reduced and experiences a DLT at the lower dose, this DLT will be attributed to the highest dose level administered.
- Dose reductions for nivolumab will not be permitted for individual subjects.

For data collection and analysis purposes, all subjects will continue to be classified by the original treatment arm.

Dose Modification Criteria for Drug-Related Adverse Events	BMS-986183 (modification at next dose)
Grade 4 neutropenia lasting > 5 days	Decrease 1 level
Grade 3 febrile neutropenia lasting > 48 hours	Decrease 1 level
Grade 4 febrile neutropenia	Discontinue
Grade 4 thrombocytopenia or ≥ Grade 3 thrombocytopenia with significant bleeding	Decrease 1 level
QTcF > 500 msec confirmed by at least 1 repeat ECG and at least 60 msec above baseline	Interrupt if needed to optimize electrolyte management. If persists after electrolyte optimization (including dose modification of BMS-986183, if necessary), discontinue.
Grade 1 Troponin I or T confirmed when repeated in 72 hours	Discontinue
Grade 3 Troponin I or T	Discontinue
AST/ALT/total bilirubin elevation per Section 4.5.3	Decrease 1 level
\geq Grade 3 infusion-related reaction	See Section 3.7
\geq Grade 3 peripheral neuropathy	Discontinue
Any other drug-related \geq Grade 3 nonhematologic AE except in subjects not receiving maximum medical management or electrolyte abnormalities that may be managed with supplements	Decrease 1 level

Table 4.5.2-1:Dose Modifications

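### Non-skin, nonhematologic, drug-related Grade 3 AEs that recur or persist get different default actions in Protocol 4.5.2 and 4.5.6, and the cross-references do not settle which section governs

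*Protocol*

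**What the plan says.** Section 4.5.6 opens with "Subjects will be required to permanently discontinue study drug for the following criteria". One entry in its list is "Any Grade 3 non-skin, drug-related AE lasting > 7 days or recurs". That entry names no Part and no drug, whereas a neighbouring entry on eye toxicity is expressly limited to Parts 3 and 4. The section closes by allowing a discussion with the medical monitor when the investigator sees a favourable benefit/risk balance for continuing.

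Section 4.5.2 contains four relevant provisions:

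- Recurrence: "If the same > Grade 3 nonhematologic AE recurs despite a dose reduction", then "a second dose reduction vs discontinuation of the subject from further protocol therapy will be discussed and agreed upon" between the sponsor or medical monitor and the investigators.
- Number of reductions: "No more than 2 dose reductions will be allowed per subject".
- Residual row of Table 4.5.2-1: any other drug-related event of at least "Grade 3 nonhematologic AE except in subjects not receiving maximum medical management or electrolyte abnormalities that may be managed with supplements" leads to a one-level decrease. The row sets no limit on duration or recurrence.
- Non-recovery: dosing is interrupted until the AE falls to Grade 1 or baseline. Therapy ends when delayed recovery "from treatment-related AEs that results in a delay of treatment for > 6 weeks", unless the parties agree otherwise.

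**The concern.** Two sections that investigators must apply to the same subject lead to different default actions. Under one, a subject whose Grade 3 event recurs or persists may continue at a lower dose. Under the other, that subject stops unless an exception is argued.

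AEs leading to discontinuation are a primary endpoint (Protocol 8.3.1, SAP 4.1). SAP 7.5 identifies them from the action taken that the site records. SAP 7.5.4 and 7.5.5 tabulate them separately from AEs leading to delay, interruption or reduction. If sites follow different sections, the same event falls into different tables, and both exposure and the apparent tolerability of a dose shift with site practice.

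**Working it through.** No figure in the plan has to be reproduced. The check applies both sections to the same event.

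**1. Where the two sections overlap.** The 4.5.6 entry is limited to Grade 3, non-skin and drug-related events. The 4.5.2 recurrence provision and the residual table row are limited to nonhematologic events. Two groups then drop out:

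- Events that Table 4.5.2-1 already marks for discontinuation. Peripheral neuropathy of Grade 3 or more is one, and the two sections agree there.
- Grade 3 laboratory abnormalities, most of which 4.5.6 exempts.

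**2. The two rules on the remaining events.**

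| Event | 4.5.2 and Table 4.5.2-1 | 4.5.6 |
|---|---|---|
| Same AE recurs after a dose reduction | Agreed choice: second reduction or discontinuation | Permanent discontinuation, subject to the closing benefit/risk discussion |
| AE lasts more than 7 days, then recovers with a treatment delay of no more than 6 weeks | Interrupt, then decrease one level | Permanent discontinuation, subject to the same discussion |

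The defaults differ in both rows. The recurrence row is the sharper conflict, because 4.5.2 expressly keeps a second reduction open. The duration row rests on the absence of a limit in the table and on the 6-week provision, since 4.5.2 never mentions 7 days.

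**3. The grade symbol.** In the available text the recurrence provision reads as strictly above Grade 3. I take it as Grade 3 or more, because Grade 4 nonhematologic AEs have their own provision in the same list. Read literally, it would not reach Grade 3. The recurrence conflict would then rest on the table row (Grade 3 or more, with no recurrence limit) and the two-reduction allowance.

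**4. Which section governs.**

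- Toward 4.5.6: Section 4.5.4 sends subjects who meet 4.5.6 to discontinuation and only the others to resumption under 4.5.2. Section 4.5.5 limits resumption to AEs that do not meet 4.5.6.
- Toward 4.5.2: Section 3.5, the list of reasons for which subjects must discontinue, refers AE-related stopping to 4.5.2. Section 3.1 names 3.5 as the place for discontinuation criteria. Section 4.5.2 itself says that permanent discontinuation is defined by its table and its own text, with no carve-out for 4.5.6.

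**5. Consistency within 4.5.6.** Section 4.5.1 makes most nonhematologic toxicity of Grade 3 or more a DLT, with listed exceptions, so many of these events also meet the DLT entries in 4.5.6. One such entry calls for stopping nivolumab and/or modifying the BMS-986183 dose. Another requires discontinuation for Grade 3 or 4 AEs meeting DLT criteria, with its own exceptions. A single event can therefore fall under a 4.5.6 entry that permits dose modification and another that requires stopping.

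**The case against.** The strongest reply is that precedence is already stated. Sections 4.5.4 and 4.5.5 both defer to 4.5.6, so the 6-week provision can be read as an outer limit for subjects who have not met a 4.5.6 criterion. The criteria in 4.5.2 are described as general guidelines. Both sections also end in a discussion with the sponsor, and discontinuation is one of the two outcomes that 4.5.2 allows on recurrence. Finally, the safety endpoints are descriptive, with no formal hypothesis testing (Protocol 1.2 and 8.5).

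Much of this stands. It eases the duration half and limits the consequence. It does not remove the conflict:

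- Section 3.5 points the other way.
- If 4.5.6 prevails, the 4.5.2 recurrence provision has little left to govern for non-skin Grade 3 AEs.
- The guideline label does not separate the sections, since 4.5.6 is also titled as guidelines and 4.5.2 contains firm limits such as the cap on reductions.
- A second reduction as an ordinary choice is not the same default as stopping unless an exception is argued.

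A reader might infer more than the documents support:

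- *That 4.5.6 leaves no way to continue.* Its closing benefit/risk discussion does.
- *That a second reduction can never occur.* Recurrent skin AEs fall outside the 4.5.6 entry, and the two-reduction allowance also covers successive different AEs.
- *That the conflict spans day 8 to day 42, about 5 weeks.* The 7 days measure how long the AE lasts. The 6 weeks (6 × 7 = 42 days) measure treatment delay in 4.5.2 and time from the previous dose in 4.5.5. These are different clocks and cannot be subtracted.
- *That the Part 2 and Part 4 enrollment triggers (29% and 31%) necessarily shift.* They count AEs requiring dose modification, and Table 4.5.2-1, titled as dose modifications, itself includes discontinuation rows. A subject with a recurrence after a reduction has already had one modification.

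**Conclusion.** The inconsistency is real but narrow. For drug-related Grade 3 AEs that are non-skin and nonhematologic, not already marked for discontinuation in Table 4.5.2-1 and not exempted as laboratory abnormalities, 4.5.2 and 4.5.6 give different default actions. The conflict is clear for recurrence. It is weaker for duration, where 4.5.4 and 4.5.5 favour 4.5.6. Precedence remains unsettled because of Section 3.5 and the DLT entry in 4.5.6 that allows modification of BMS-986183.

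The practical consequence is that one event may be counted as a dose reduction at one site and as an AE leading to discontinuation at another. The size cannot be stated, because the documents give no incidence for such events. The planned total of about 151 subjects is the population to which the rules apply, since the 4.5.6 entry names no Part. It is not an estimate of how many would be affected.

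The recurrence half assumes that the grade symbol in 4.5.2 means Grade 3 or more. This merits correction as a wording inconsistency and does not invalidate the planned analyses.

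**What to change.** Reconcile the duration and recurrence entry and the DLT entries of 4.5.6 with three other places: the 4.5.2 recurrence provision (confirming its grade symbol), the residual row of Table 4.5.2-1, and the cross-reference in 3.5. State in both 4.5.2 and 3.5 which section governs, for which drug (BMS-986183, nivolumab or both) and in which Parts. The choice of clinical rule belongs to the sponsor and investigators, and none is proposed here.

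The cost is protocol wording in one amendment. The SAP definitions need no change, because they already rely on the recorded action.
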